## **Appendix 6**

### **Childbearing Potential, Pregnancy Testing, and Contraception**

All females of childbearing potential (including those who have had a tubal ligation) will have a serum pregnancy test at screening and a urine pregnancy test prior to administration of study drug at subsequent visits. If a urine pregnancy test result is positive, study drug will not be administered until pregnancy is ruled out. The result must be confirmed by a serum pregnancy test (conducted by the central laboratory). See Section 5.4.3 of the protocol for management of a patient with a confirmed pregnancy.

All postpubertal female patients are considered to be of childbearing potential unless they meet one of the following criteria:

- The patient has been postmenopausal (non-therapy-induced amenorrhea) for at least 12 months
- The patient had a surgical bilateral oophorectomy (with or without hysterectomy) more than 6 weeks prior to enrollment
- The patient had a hysterectomy

Female patients of reproductive or childbearing potential who are unwilling to use a highly effective method of contraception or remain abstinent during the treatment period and for at least 24 weeks after the last dose of study drug will be excluded from study participation.

Abstinence is acceptable only if it is in line with the preferred and usual lifestyle of the patient. Periodic abstinence (e.g., calendar, ovulation, symptothermal, or postovulation methods) and withdrawal are not acceptable methods of contraception.

Examples of highly effective contraception include the following:

- Combined oral contraceptive pill
- Contraceptive transdermal patch
- Intrauterine device
- Implants for contraception
- Injections for contraception (with prolonged release)
- Hormonal vaginal device
- Sterilization, surgical tubal ligation
- Sole sexual partner consisting of surgically sterilized male partner with appropriate postsurgical verification of the absence of spermatozoa in the ejaculate

## **Appendix 6** **Childbearing Potential, Pregnancy Testing, and Contraception** **(cont.)**

- Double-barrier methods: condom and occlusive cap (diaphragm or cervical/vault caps) with spermicidal foam/gel/film/cream/suppository (Note: a female condom and male condom should not be used together because friction between the two can result in either product failing)

Patients may provide verbal confirmation that the partner completed appropriate follow-up after vasectomy. Sites are not required to obtain partner medical records.

With female partners of childbearing potential or pregnant female partners, men must remain abstinent or use a condom during the treatment period and for at least 24 weeks after the last dose of study drug. Men must refrain from donating sperm during this same period.

For men and women: The reliability of sexual abstinence should be evaluated in relation to the duration of the clinical trial and the preferred and usual lifestyle of the patient. Periodic abstinence (e.g., calendar, ovulation, symptothermal, or postovulation methods) and withdrawal are not acceptable methods of contraception.

## Appendix 7

### Worksheet for the PML Neurologic Examination

#### **PML Subjective Checklist of neurologic assessment to monitor for progressive multifocal leukoencephalopathy (PML) in the Etrolizumab Pediatric Studies**

PML usually manifests with subacute, progressive neurologic deficits including:

Neurologic Domain	Signs/Symptoms	Relevant PML Subjective Checklist Question
Altered mental status	Can encompass a variety of presenting signs and symptoms including cognitive changes (confusion, difficulty concentrating, memory loss) and altered behavior (including personality changes)	Q2, Q5, Q6
Higher cortical dysfunction	Impaired comprehension and/or formulation of language (aphasia), loss of ability to recognize objects, persons, sounds, shapes, or smells (agnosia)	Q2, Q5, Q6
Visual changes	Loss of visual fields (homonymous hemianopsia), double vision (diplopia)	Q1
Motor deficits	Weakness (hemiparesis or monoparesis), seizures (generalized or partial), difficulties with speech (dysarthria) or swallowing (dysphagia)	Q2, Q3
Sensory deficits	Sensory loss (i.e. paresthesia)	Q7
Coordination	Difficulty walking and maintaining balance (ataxia), lack of voluntary coordination of limb movement (limb ataxia)	Q4

In order to monitor patients for PML, a systematic review of symptoms seeking any new neurological deficits will be performed with the patient and parents. Significant new symptoms should trigger referral to a pediatric neurology specialist to confirm and investigate.

**At screening and all other visits** the PML Subjective Checklist should be performed.

During the evaluation, if there is a “yes” response to the questions, the symptoms of the patient should be discussed with the patient or patients parent/legal guardian to confirm that these are new and significant changes that cannot be ruled out by every day events.

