**Table 4 Guidelines for Management of Patients Who Experience Specific Adverse Events (cont.)**

Event	Action to Be Taken
Signs and symptoms of possible PML	
 
• If a patient has a positive finding on the PML Subjective Checklist, or if there is strong clinical suspicion for PML, then the investigator is required to follow the process described in the PML algorithm (see Appendix 8). If PML is suspected, a neurology consultation should be promptly arranged. Based on this evaluation, brain magnetic resonance imaging and cerebral spinal fluid JCV analysis may be performed (see Appendix 8).
 
• Investigators and HCPs should also be trained to accurately and appropriately report these events immediately to the Sponsor as adverse events of special interest and as serious adverse events, if appropriate (see Section 5.4).
 
• The following are signs and symptoms that may potentially indicate PML: 
 
• Alteration in mental status (cognitive changes, including confusion, difficulty concentrating, memory loss) and altered behavior (including personality changes)
 
• Higher cortical dysfunction, including impaired comprehension and/or formulation of language (aphasia), loss of ability to recognize objects, persons, sounds, shapes, or smells (agnosia)
 
• Visual changes, including loss of visual fields (homonymous hemianopsia), double vision (diplopia)
 
• Motor deficits, including weakness (hemiparesis, monoparesis), seizures, (generalized or partial), difficulties with speech (dysarthria,) or swallowing (dysphagia)
 
• Sensory deficits, including sensory loss (paresthesias)
 
• Coordination deficits, including difficulty walking and maintaining balance (ataxia), lack of voluntary coordination of limb movement (limb ataxia)
 
 
 
• If PML is suspected then all investigational treatment should be withheld in that patient and may only be restarted if it is confirmed that the patient does not have PML.
 

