- g For patients that complete the OLE *treatment*, the PML monitoring phase includes 104 weeks of PML safety monitoring.
- h Unscheduled visit represents a visit that is not as per Schedule of Assessments and it is symptom driven.
- i If there are any signs or symptoms suggestive of PML identified on the subjective checklist during the telephone call, the patient will be asked to come into the clinic for further evaluation and if indicated referral to a neurologist. .
- j Investigators are not required to actively monitor patients for adverse events; however, if he or she becomes aware of any other serious adverse events that are believed to be related to prior study drug treatment, these should be reported directly to Roche or its designee either by faxing or by scanning and e-mailing the Serious Adverse Event/Adverse Event of Special Interest Reporting Form with use of the fax number or e-mail address provided to the investigators. The investigator may become aware of such events at these timepoints or via other means, but the data are not to be collected routinely.

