**Appendix 7**  
**Worksheet for the PML Neurologic Examination (cont.)**

**PML Subjective Checklist**

Symptoms	“Compared to how you (your child) usually feel, have you (your child) had a significant change in any of the following?”		If the answer is “Yes”, obtain a description of the symptom(s) with examples
	YES	NO	
1) Have you (your child) experienced any new difficulty with vision (ex. Blurred vision or seeing double), new difficulty with reading, or loss of vision?			
2) Have you (your child) had new onset difficulty speaking, understanding, or communicating. (e.g., word finding trouble, using the wrong words)			
3) Have you (your child) been experiencing new onset weakness in face, arms and/or legs?			
4) Has your child recently developed clumsiness, difficulty with balance, or falling more than normal?			
5. Has your child recently developed difficulty understanding others, or been less aware of the environment?			

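### The PML Subjective Checklist has no question on seizures or swallowing, although Appendix 7 assigns the domain that lists both signs to Q2 and Q3

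*Combined protocol and SAP*

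**What the plan says.** The sign table in Appendix 7 sets out neurologic domains, the signs in each, and the relevant checklist questions. Its motor-deficits row reads "Weakness (hemiparesis or monoparesis), seizures (generalized or partial), difficulties with speech (dysarthria) or swallowing (dysphagia" and gives Q2 and Q3. Table 4 (Section 5.1.2.1), which tells investigators what may indicate PML, carries the same list: "Motor deficits, including weakness (hemiparesis, monoparesis), seizures, (generalized or partial), difficulties with speech (dysarthria,) or swallowing (dysphagia".

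The two questions assigned to that row are:

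- Q2: "Have you (your child) had new onset difficulty speaking, understanding, or communicating. (e.g., word finding trouble, using the wrong words"
- Q3: "Have you (your child) been experiencing new onset weakness in face, arms and/or legs"

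Footnotes to Appendices 1a to 1d define the scheduled PML neurologic examination as the checklist and nothing more. Appendix 1e, footnote a, has the checklist given by telephone in the PML monitoring phase. Footnote j to the same appendix adds: "Investigators are not required to actively monitor patients for adverse events". The sole endpoint of that phase is confirmed PML (Table 3).

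**The concern.** A sign table that assigns questions to each domain invites the reader to assume that the questions reach the signs in that domain. For the motor row they reach only half of them. The mapping is by domain, so coverage of each sign is implied rather than stated, but no footnote says that seizures and swallowing are to be asked about in some other way.

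This matters because the checklist carries the scheduled part of PML surveillance. It is used at screening, where a clinically significant abnormality excludes the patient (Section 4.1.2.5), at clinic visits, and on the monitoring calls. Under Section 3.1, a sign or symptom picked up on the checklist during a call is what brings the patient in for a neurologic examination. PML has to be suspected before it can be confirmed, and a child whose only new problem is a seizure or difficulty swallowing could truthfully be recorded as No on all seven items.

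**Working it through.** No arithmetic underlies the plan's text here, so the check is a comparison of wording followed by a count of the phases affected.

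**Step 1: each motor sign against all seven questions (Appendix 7).** Q1 is about vision ("Have you (your child) experienced any new difficulty with vision"). Q4 is about coordination ("Has your child recently developed clumsiness, difficulty with balance, or falling more than normal"). Q5 covers comprehension and awareness of surroundings, Q6 behavior and cognition, and Q7 sensation.

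| Sign in motor row | Question that names it | Indirect chance elsewhere |
|---|---|---|
| Weakness | Q3 | not needed |
| Speech difficulty | Q2 | not needed |
| Seizures | none | some, through Q5 (reduced awareness) or Q4 (falls) |
| Swallowing difficulty | none | only if facial weakness is also present (Q3) |

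Signs with a matching question: 2 of 4. Signs without one: 4 − 2 = 2. Questions that name seizures or swallowing: 0 of 7. Neither Q4 nor Q5 is assigned to the motor row.

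**Step 2: what else is scheduled in each phase.**

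- *Randomized phase and open-label extension*, up to 24 + 312 = 336 weeks. Adverse events are sought at each contact (Section 5.3.1) with open questions about new health problems (Section 5.3.2). Physical examinations after screening are symptom-driven (Section 4.5.4).
- *12-week follow-up after the extension*. Adverse events are collected at Weeks 4, 8 and 12, and the checklist is given at Week 12 (Appendix 1d).
- *Remainder of the 104-week PML monitoring period*. The checklist by telephone is the only scheduled active assessment. From Section 3.2 and Appendix 1e, footnotes c and e, the length of this remainder is:
  - after the extension: 104 − 12 = 92 weeks;
  - after completing the randomized phase only: 104 − (4 + 8) = 92 weeks;
  - after early discontinuation from the randomized phase: 104 − 8 = 96 weeks.

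**Step 3: is there a separate structured review?** Appendix 7 speaks of reviewing symptoms for new neurological deficits with the patient and parents. It then introduces the checklist, and no schedule row or form records a review apart from it. The PML eCRF fields in Appendix 7 record whether and when the checklist was given, whether it showed clinically significant abnormalities, and whether PML is suspected.

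**Step 4: size of the effect.** The documents do not say how often PML presents with seizures or swallowing difficulty alone. No sensitivity or missed-case figure can be derived.

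**The case against.** The strongest reply is that the checklist is one of several ways in. Strong clinical suspicion starts the PML algorithm without a positive checklist (Table 4, Appendices 7 and 8), and Table 4 tells investigators that seizures and dysphagia count. Alert cards ask families to report any new or worsening neurological abnormality at once (Section 5.1.1.1.1). Appendix 7 asks for a wider symptom review. Adverse events are asked about on treatment and in the 12-week follow-up. Unscheduled symptom-driven calls exist (Appendix 1e), and suspected PML is notifiable for 2 years after the last dose (Section 5.6). Footnote j goes on to speak of other serious adverse events, so it limits general event collection and not PML surveillance itself.

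All of this stands, and it limits the point. A reader might infer that the checklist is the only instrument behind the PML endpoint, or that the plan cannot detect these two signs. The documents do not support either reading. The endpoint is confirmed PML, reached through a neurologist and, if PML cannot be ruled out, an adjudication committee with possible MRI and CSF testing. Q4 or Q5 could also catch some seizures.

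What the reply does not remove is the mismatch within Appendix 7. The remaining routes depend on someone volunteering or recognizing the symptom, and a structured screen exists to reduce that dependence. This matters most on the monitoring calls, where general adverse event questioning no longer fills the gap, and for swallowing, which has no comparable indirect item.

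**Conclusion.** The point holds as a mismatch between the sign table and the questionnaire: 2 of the 4 listed motor signs are not asked about, and the motor-row mapping to Q2 and Q3 is incomplete as written. The practical gap is narrow on treatment and in the 12-week follow-up. It is clearest in the final 92 to 96 weeks of telephone monitoring, for about 24 planned patients.

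It would go too far to conclude that a finding of no PML would be invalid, or that a new seizure would probably be missed; many would reach medical attention anyway. The protocol reports no PML case with etrolizumab to date, and about 24 children can say little about PML risk under any checklist wording. The primary pharmacokinetic and pharmacodynamic endpoints are unaffected. The conclusion assumes that the seven questions are used as printed and that no unlisted prompt on these signs exists in a site manual.

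**What to change.** Reconcile the Appendix 7 sign table with the checklist so that every listed sign is elicited by a question:

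- add a checklist item covering new seizures and new swallowing difficulty;
- correct the motor row so that it points to that item as well as to Q2 and Q3;
- use the same version at clinic visits and on monitoring calls, and update the worksheet and eCRF to match.

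The existing referral and dosing-suspension rules stay unchanged. The cost is one more item on a seven-item worksheet and a few more non-specific positive answers to triage. Appendix 7 already has a step for discussing each positive answer with the family before it is judged new and significant.

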**Appendix 7**  
**Worksheet for the PML Neurologic Examination (cont.)**

**PML Subjective Checklist**

Symptoms	“Compared to how you (your child) usually feel, have you (your child) had a significant change in any of the following?”		If the answer is “Yes”, obtain a description of the symptom(s) with examples
	YES	NO	
1) Have you (your child) experienced any new difficulty with vision (ex. Blurred vision or seeing double), new difficulty with reading, or loss of vision?			
2) Have you (your child) had new onset difficulty speaking, understanding, or communicating. (e.g., word finding trouble, using the wrong words)			
3) Have you (your child) been experiencing new onset weakness in face, arms and/or legs?			
4) Has your child recently developed clumsiness, difficulty with balance, or falling more than normal?			
5. Has your child recently developed difficulty understanding others, or been less aware of the environment?			

**Appendix 7**  
**Worksheet for the PML Neurologic Examination (cont.)**

6. Has your child experienced change in behavior, or new problems with attention, recall, memory, or thinking?			
7. Have you (your child) been experiencing any new numbness or other loss of sensation?			

**Please refer to the PML Algorithm in the Protocol Appendix for details.**

- If there is a clinically significant abnormal finding on the PML Subjective Checklist, this should be appropriately documented on the worksheet and in the eCRF.
- If there are any clinically significant abnormalities found on the PML Subjective Checklist or if there is high clinical suspicion for PML (in the opinion of the investigator):
  - This must be reported as an adverse event of special interest (AESI) within 24 hours
  - An urgent referral to a neurologist should be made.
  - Dosing with study drug will be suspended until PML can be ruled out.
  - Further evaluation will proceed according to the PML Algorithm in the Protocol Appendix.
  - Any confirmed diagnosis of PML should be reported as a serious adverse event (SAE).

**Please complete the PML eCRF.**

Was the PML Subjective Checklist administered? (Yes/No)

If yes, date of administration of PML Subjective Checklist (Date)

[figure not shown]
If yes, were there any clinically significant abnormalities on the PML Subjective Checklist? (Yes/No)

Is PML suspected? (Yes/No)

## Appendix 8

### Algorithm for Evaluation of Progressive Multifocal Leukoencephalopathy

- If there is a clinically significant positive finding on the PML Subjective Checklist, this should be appropriately documented.
- If there are any clinically significant abnormalities found on the PML Subjective Checklist or if there is high clinical suspicion for PML (in the opinion of the investigator):
  - Report as an AESI within 24 hours
  - Urgently refer the patient to a neurologist
  - Suspend dosing of drug until PML can be ruled out

## Appendix 9

### Clinical Criteria for Diagnosing Anaphylaxis

These criteria are taken from a summary report from the second symposium on the definition and management of anaphylaxis, conducted by the National Institute of Allergy and Infectious Disease/Food Allergy and Anaphylaxis Network. Anaphylaxis is highly likely when any one of the following three criteria is fulfilled:

1. Acute onset of an illness (minutes to several hours) with involvement of the skin, mucosal tissue, or both (e.g., generalized hives, pruritus or flushing, swollen lips-tongue-uvula)

AND AT LEAST ONE OF THE FOLLOWING:

- Respiratory compromise (e.g., dyspnea, wheeze-bronchospasm, stridor, reduced peak expiratory flow, hypoxemia)
- Reduced blood pressure or associated symptoms of end-organ dysfunction (e.g., hypotonia, syncope, incontinence)

2. Two or more of the following that occur rapidly after exposure to a likely allergen for that patient (minutes to several hours):
  - Involvement of the skin-mucosal tissue (e.g., generalized hives, itch-flush, swollen lips-tongue-uvula)
  - Respiratory compromise (e.g., dyspnea, wheeze-bronchospasm, stridor, reduced peak expiratory flow, hypoxemia)
  - Reduced blood pressure or associated symptoms (e.g., hypotonia, syncope, incontinence)
  - Persistent gastrointestinal symptoms (e.g., crampy abdominal pain, vomiting)
3. Reduced blood pressure after exposure to known allergen for that patient (minutes to several hours):
  - Infants and children: low systolic blood pressure (age specific) or greater than 30% decrease in systolic blood pressure
  - Adults: systolic blood pressure of less than 90 mmHg or greater than 30% decrease from that person's baseline

---

 Low systolic blood pressure for children is defined as less than 70 mmHg from 1 month to 1 year, less than (70 mmHg + [2 x age]) from 1 to 10 years, and less than 90 mmHg from 11 to 17 years.
